**Statistical Analysis Plan for DIVE-I study :**  
**Dopaminergic restauration controlled by intraVEentriculaire**  
**administration.**

**Version : 2.0      Date: 28/05/2024**

This document is written according to Guidelines for the Content of Statistical Analysis Plans in Clinical Trials. (1)

**Trial registration:** 2020-000155-12

**Protocol version:** The SAP has been written based on information contained in the study protocol version 7, dated 31 May 2022.

**SAP revision history :** no SAP history

Protocol Version	SAP version no.	Section number changed	Description of and reason for change	Date
7.0	1.0	NA	First SAP version signed	16/05/2023
7.0	2.0	5.1 Outcome definitions  5.1.2 Phase II  Secondary outcomes  Exploratory outcomes	Revised the change after data-blind review (22/04/2023):  Moving exploratory as secondary outcome: 'Fluctuation dyskinesia score'  Adding secondary outcome: 'Time in good autonomy' Move secondary as exploratory outcome : 'Clinical global impression of patient and investigator', 'the 50th percentile of the available	28/05/2024

		
5.2 Analysis methods
 
bradykinesia score', 'the 50th percentile of the available dyskinesia score'
 
All analysis for phase II party of study are revised regarding the limited number of sample size (n=9) by comparison to the planned sample size (n=20).
 
Primary outcome efficacy analysis will be performed a non-parametric paired test, and by reported a case-report descriptive analysis. All secondary and exploratory quantitative outcomes will be analyzed using descriptive analysis without statistical test.
	
--	--	---	--

## List of Abbreviations

Abbreviations	Label
AIMS	Abnormal Involuntary Movement Score
BKS	Bradykinesia score
CGI	Clinical Global Impression
CI	Confidence limit
DKS	Dyskinesia score
DRS	Dyskinesia rating scale
ECG	Electrocardiogram
eCRF	Electronic case report form
ECMP	Echelle comportemental Maladie de Parkinson (behaviour scale for Parkinson's disease)
FDS	Fluctuation and dyskinesia score
GKC	Global Kinetics Corporation
HVA	Homovanillic acid
ICV	Intracerebroventricular
LARS	Lille Apathy rating scale
MDS-UPDRS	Movement Disorder Society-sponsored revision of the Unified Parkinson's Disease Rating
MRI	Magnetic resonance imaging
MOCA	Montreal Cognitive Assessment
NPI	Neuropsychiatry Inventory
PAS	Parkinson Anxiety Scale
PDQ39	Parkinson's Disease Questionnaire
PKG	Parkinson KinetoGraph
PTI	Percentage of time of immobility
PTO	Percent Time Over target
PTT	Percentage of time with a tremor

## 1 INTRODUCTION

### 1.1 Background and rational

Parkinson's disease is characterized by cerebral dopamine depletion. Dopamine cannot be administered orally. On the model of the insulin pump in diabetes, we want to restore the natural circadian cycle of dopamine at the cerebral level by administering it at the intra-ventricular level. This is done according to the classic neurosurgical intervention of ventricular bypass by implanting a delivery system by a fine catheter connected subcutaneously to a high-tech pump placed at the intra-abdominal level already on the market. The adjustment of the pump by telemetry makes it possible to adapt hour by hour the exact need of each patient. The objective of bi-monthly filling avoids oral intake of L-dopa every two to three hours, ensuring perfect ergonomics. This therapeutic concept has already been carried out in two patients in 1984 and 1989, revealing very good tolerance and efficacy. At that time the patients treated were fragile with dementia and psychosis and no precautions were taken for the deleterious auto-oxidation of dopamine; however, tolerance was good and efficacy was clearly reported. However, this was not pursued for fear of the deleterious oxidation of dopamine, the wrong indication (too advanced patients with dementia and severe hallucinations) and above all responsible for an exhaustion of the effect (tachyphylaxis). The exhaustion being due to the wrong indication, to a constant dose (instead of respecting the circadian rhythm of dopamine) and especially to the oxidation of the latter.

Given the need to perform a brief neurosurgical intervention (30 to 60 minutes, similar to ventricular bypass but with rigorous intraoperative identification using preoperative MRI) with the installation of a medical device, we carry out a proof-of-concept study in three phases: a first safety phase (phase I) with administration of intracerebroventricular dopamine (intervention) according to a very careful slow titration protocol including one patient at a time up, a second efficacy phase II study using a cross-over design, and a long term follow-up phase of patients treated with intervention. This three-phases strategy will make it possible to guarantee the precautionary principle by progressively exposing the fewest patients while then allowing patients who undergo this intervention to benefit from this therapeutic procedure while providing the first reliable data on safety and efficacy.

## **1.2 Research hypothesis**

The hypothesis of phase I trial is that, in Parkinson's disease in the stage of severe motor and non-motor complications related to L-dopa, the administration of intracerebroventricular dopamine is safe regarding the occurrence of serious adverse event. The hypothesis of phase II trial is that, in Parkinson's disease in the stage of severe motor and non-motor complications related to L-dopa, there is an increase in the Percent Time Over target (PTO) in the intervention phase (A-dopamine intracerebroventricular) by comparison to the control phase (usual optimized oral medical treatment). The hypothesis of long-term follow-up phase trial is the maintenance of efficacy on motor and non-motor complications.

## **1.3 Study Objectives**

### ***Phase I study:***

The primary objective is to determine the feasibility and the safety of administration of intracerebroventricular (ICV) dopamine.

### ***Phase II study:***

The primary objective is to determine the efficacy (superiority) of administration of intracerebroventricular (ICV) dopamine in combination of oral L-dopa at optimized dose versus usual optimized oral medical treatment in combination with ICV Placebo for improving PTO in patients with Parkinson's disease in the stage of severe motor and non-motor complications related to L-dopa.

Secondary objectives are:

1) to assess the efficacy of administration of ICV dopamine in combination of oral L-dopa at optimized dose versus usual optimized oral medical treatment in combination with ICV Placebo on:

- motor aspects
- cognitive-behavioural aspects: drowsiness, anxiety, depression, apathy, sleep, hallucinations
- cognition and psychiatric assessment
- quality of life
- general condition

2) To assess the tolerance of administration of intracerebroventricular dopamine versus usual optimized oral medical treatment alone

- 3) To assess the psychiatric tolerance of administration of intracerebroventricular dopamine versus usual optimized oral medical treatment alone

***Long term follow-up study:***

The primary objective is to assess the maintenance of efficacy of long-term continuous administration of intracerebroventricular dopamine on motor control and non-motor complications.

Secondary objectives are

- 1) To assess the maintenance of efficacy on:

- motor aspects
- cognitive-behavioural aspects: drowsiness, anxiety, depression, apathy, sleep, hallucinations
- cognition and psychiatric assessment
- quality of life
- general condition

- 2) To assess the maintenance of tolerance of intracerebroventricular dopamine administration

## 2 TRIALS METHODS

### 2.1 Trial design

DIVE-1 is a proof of concept study with three phases:

- a first safety phase (phase I) with administration of intracerebroventricular dopamine (intervention) according to a very careful slow titration protocol.
- a second efficacy phase II study (including patients enrolled in phase I who reached the titration objective without complications) using a randomized 2x2 cross-over design with administration of intracerebroventricular dopamine as intervention condition and usual optimized oral medical treatment alone as control condition
- a long-term follow-up phase of ICV dopamine administration restricted to patients enrolled in phase II study.

Each study phase is fully detailed in study protocol, according to study flow provided in figure 1.

Briefly, in first safety phase I, a slow titration of intracerebroventricular dopamine administration including one to one (namely, the second patient will be included after the end of titration period of the first patient, and so on) and with an independent Monitoring Committee who will review all adverse events.

The following go no go safety rule is applied to go to phase II:

- 1) for the first 5 patients, if no or at most one serious and unexpected adverse events (apart from the rare surgical risks of haemorrhage and infection with no impact in vital and functional prognosis of the patient) is observed, 15 other patients may be included and phase II will be start.
- 2) If two or more serious or unexpected adverse events (apart from the rare surgical risks of haemorrhage and infection with no impact in vital and functional prognosis of the patient) occur in first five patients, only 5 new patients could be included, and the following rule will be proposed to the independent Monitoring Committee:
  - if no or at most one of serious and unexpected adverse events among the 5 new patients, 10 other patients will be included in phase I and phase II can be started

[figure not shown]
- if two or more serious or unexpected adverse events among the 5 new patients, the Independent Monitoring Committee could decide to stop the study.

During phase I, Independent Monitoring Committee will be aware for each unexpected adverse events one patient at a time up and can propose to stop the study at any time.

In second efficacy phase II, 20 patients will be enrolled after terminating the titration phase I without complications and randomized in two groups according to cross-over design of 2 treatment periods of 4 weeks separated by a therapeutic switch carried out in the hospital. The previous treatment will be stopped at the end of period 1 and replaced by the new treatment, after 3 weeks of washout. During the 2 treatment periods and washout period, the patients will be treated by oral L-dopa at optimized dose. In summary, patients will be randomized into two groups according to the following treatment sequences:

- group 1 (n=10): period 1(ICV dopamine treatment + oral L-dopa at optimized dose) vs. period 2 (oral treatment at optimized dose + ICV Placebo treatment)
- group 2 (n=10): period 1: (oral treatment optimized + ICV Placebo treatment) vs. period 2 (ICV dopamine treatment + oral L-dopa at optimized dose)

At the end of phase II, all patients are invited to continue to use ICV dopamine treatment over the long term with the dose that allows satisfactory motor control (less than 1 hour of moderate or severe off per day and less than half an hour of dyskinesia) with or without a minimal residual dose of oral dopaminergic therapy.

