## 5.2 Analysis methods

### 5.2.1 Phase I

A case-report analysis will be done for phase I part of DIVE-1 study, with the following safety go no go rule: 1) In no or at most one serious and unexpected adverse events (apart from the rare surgical risks of haemorrhage and infection with no impact in vital and functional prognosis of the patient) in the first five patients, 15 other patients may be included in Phase I and the phase II will be start.

2) If two or more serious or unexpected adverse events (apart from the rare surgical risks of haemorrhage and infection with no impact in vital and functional prognosis of the patient) occur in first five patients, only 5 new patients could be included, and the following rule will be proposed to the independent Monitoring Committee to start the phase II:

- in the no or at most one serious and unexpected adverse events in the 5 new patients, 10 other patients may be included in Phase I and phase II will be start.

- if two or more serious or unexpected adverse events, the Independent Monitoring Committee could decide to stop the study without start the phase II trial.

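### The phase I go/no-go rule counts different events in its two branches, so the same events could be reported as meeting both go and restrict

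*SAP*

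**What the plan says.** SAP section 2.1 sets a two-step safety rule.

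- **First five patients.** Go applies "if no or at most one serious and unexpected adverse events" are seen. The trial is restricted to five new patients "If two or more serious or unexpected adverse events" occur. Both branches set aside the same surgical haemorrhages and infections, namely those that do not affect the patient's vital or functional prognosis.
- **Five new patients, if restricted.** Go applies "if no or at most one of serious and unexpected adverse events among the 5 new patients". The committee may stop the study "if two or more serious or unexpected adverse events among the 5 new patients".

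Section 5.2.1 makes the rule part of the phase I analysis: "A case-report analysis will be done for phase I part of DIVE-1 study, with the following safety go no go rule". Its go conditions are "In no or at most one serious and unexpected adverse events" and, at the second look, "in the no or at most one serious and unexpected adverse events in the 5 new patients". Its restrict and stop conditions again join the two attributes with *or*.

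Other sections bear on the weight of this. Section 2.1 also says that the committee "can propose to stop the study at any time". Section 5.1.1 makes the phase I primary outcome a committee assessment of adverse effects, with a list of complications to consider. Section 2.3 records a cap of 12 patients from February 2023 and 9 patients with complete phase II primary data. Section 2.5 refers to the protocol and back to section 2.1 for the stopping guidance.

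**The concern.** At most one and two or more are complements only if they count the same events. Here the go branch counts events that are serious *and* unexpected, while the restrict or stop branch counts events that are serious *or* unexpected. The second set contains the first, so some outcomes satisfy both conditions.

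The events in dispute matter to the phase I question. Section 1.2 states the phase I hypothesis in terms of serious adverse events, with no requirement that they be unexpected. A serious but expected event never counts towards the *and* total and always counts towards the *or* total, unless the surgical exclusion removes it.

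Section 2.4 plans no phase I tests, only description together with this rule. If the phase I report says that the criterion was met, a reader needs to know which count was used. As written, that choice could be made after the events are known.

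**Working it through.** The SAP gives no event rate or operating characteristic for the rule, so there is no figure to reproduce. The check is one of logic.

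**Inputs.** The branch conditions in sections 2.1 and 5.2.1, after the surgical exclusion. In a cohort of five patients, let

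- a = events both serious and unexpected,
- b = events serious but expected,
- c = events unexpected but not serious.

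**Conditions as written.** Go: a ≤ 1. Restrict or stop: a + b + c ≥ 2.

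**Gap.** An outcome meeting neither branch would need a ≥ 2 and a + b + c ≤ 1, which is impossible. There is no gap.

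**Overlap.** Both branches are met exactly when a ≤ 1 and a + b + c ≥ 2.

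| (a, b, c) | *and* count | *or* count | Branch met |
|---|---|---|---|
| (0, 1, 0) | 0 | 1 | go only |
| (0, 2, 0) | 0 | 2 | both |
| (0, 0, 2) | 0 | 2 | both |
| (1, 1, 0) | 1 | 2 | both |
| (1, 0, 1) | 1 | 2 | both |
| (2, 0, 0) | 2 | 2 | restrict or stop only |

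**Enumeration.** Let each of a, b and c run from 0 to 3, giving 4 × 4 × 4 = 64 combinations.

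- Restrict or stop only (a = 2 or 3): 2 × 16 = 32.
- Go only (a + b + c ≤ 1): 4, namely (0,0,0), (1,0,0), (0,1,0) and (0,0,1).
- Both: 64 − 32 − 4 = 28.
- Neither: 0.

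These are logical cases, not probabilities. They show that the overlap is not confined to odd corners, but say nothing about how likely it was.

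**After correction.** With one definition throughout, the conditions become a ≤ 1 against a ≥ 2, or a + b + c ≤ 1 against a + b + c ≥ 2. Either pair is an exact complement, with no overlap and no gap.

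**Extent in the text.** There is one mismatch, present at two looks and stated in two sections: 2 × 2 × 2 = 8 branch statements, with *and* in all four go statements and *or* in all four restrict or stop statements. The repetition shows that the wording is stable. It does not multiply the problem.

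**The case against.** The strongest reply is that the conflict is only verbal. The second-look wording "if no or at most one of serious and unexpected adverse events among the 5 new patients" can be read as at most one among the serious events and the unexpected events taken together. That is the *or* set, and the branches then become complements, as the author presumably intended. This reading is possible, but the text does not force it. The first-look wording "if no or at most one serious and unexpected adverse events" more naturally describes events with both attributes, and nothing in the SAP chooses between the readings.

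A second reply is that the protocol, to which sections 2.1 and 2.5 refer, may settle the definition. It may, and the fix starts there. But the SAP states the rule in full twice, so this is an inconsistency in what it says and not a detail left to another document.

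Two stronger readings are tempting, and the SAP does not support either.

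- *That phase I stands or falls on this rule alone.* Section 5.1.1 makes the primary outcome a committee assessment of adverse effects, with a list of complications. The committee reviews all adverse events and "can propose to stop the study at any time". The second-look rule is put to it as a proposal, and the stop is discretionary.
- *That the wording still decides how many patients are exposed.* The written consequences are 15 further patients against 5 at the first look, and 10 further patients against a possible stop at the second. SAP 2.0 was written after phase II primary data had been collected, under the 12-patient cap of section 2.3. If that cap also limits phase I entry, which is an assumption, at most 12 − 5 = 7 patients could follow the first look and 12 − 10 = 2 the second. The figures of 15 and 10 are therefore probably no longer live.

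**Conclusion.** The point holds in a limited form. Read literally, the go and restrict or stop branches overlap at both looks whenever there are at least two serious-or-unexpected events of which at most one is both. The SAP does not say which count governs. The same phase I events could then be reported as meeting go and as meeting restrict.

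The remaining effect is on whether the phase I report can state that the go criterion was met. Patient exposure, tests, estimates and analysis populations are not affected.

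Whether the conflict arose in fact cannot be told, because the SAP gives no phase I event counts. With no counted event, one counted event, or at least two that are both serious and unexpected, the two readings agree. Any probability of conflict would rest on assumed event rates, so none is given. The conclusion assumes only that *and* and *or* carry their ordinary meaning. The correction is worth making because it is cheap and concerns a safety threshold.

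**What to change.** Use one event definition in all branch statements of sections 2.1 and 5.2.1. Take it from the protocol or from the committee's records made at the time of the decision, and do not choose it in the light of the observed events.

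In the phase I case report, classify each event as serious yes/no and unexpected yes/no, note any event set aside under the surgical exclusion, and state whether go holds under both the *and* count and the *or* count. If neither source settles the definition, say so and report both counts.

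The cost is a wording change in two sections, a check against existing records, and one small table. No new data are needed.

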## 2.2 Randomisation

For the phase II part of the DIVE-1 study, patients are randomized in 2 treatment sequences according to a balanced plan (1:1) by using a randomization list generated by computer and provided by an independent statistician of CHU of LILLE. The randomization list will be implemented into the eCRF developed with Clinsight software. Patients will be randomized as soon as possible after having completed the phase I part of study (patients reached, at this time, a balanced titration established within 9 weeks).

## 2.3 Sample size

Full details of the sample size are described within the clinical trial protocol and was determined according to the phase II part of study. We planned to dispose to 20 patients analysable (who completed the two-treatment sequence in phase II without major protocol deviations) to have a power >80% to detect, with a two-sided test at 0.05 significance level, an absolute decrease in PTO of 10% in intervention period compared to control period, by assuming a standard deviation of 15% and a correlation of 0.5 between the repeated measures.

The sample size was revised in 23 February 2023 following an amendment regarding the ability of central pharmacy of Lille university hospital to ensure the weekly production of experimental treatment in safe condition for a maximum of 12 patients. Regarding the proof of concept phase II study, the number of 12 patients was considered acceptable to provide first evidences of efficacy (by interpreting effect size on primary outcome and by a detailed descriptive analysis of changes in secondary outcomes in each period). During the data blind review, only 9 patients have available complete data on primary outcome and could be analysed.

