#### **2.4 Framework**

Primary and secondary comparative objectives of phase II part of DIVE-1 trial are tested for superiority in favour of intervention versus control treatment period. For phase I study, none statistical tests will be done and only descriptive analysis with go no go rule for safety will be done. For long term follow-up phase, intra-patient comparisons will be done to assess the maintenance efficacy and safety.

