### **3 STATISTICAL PRINCIPLES**

#### **3.1 Confidence intervals and p-values**

All applicable statistical tests will be 2-sided and will be performed using a 5% significance level.

No statistical comparisons will be done for secondary objectives, only a descriptive analysis will be performed and we will report standardized differences between active and control period as effect sizes.

All confidence intervals (CIs) presented will be 95%CI and 2-sided.

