***Primary outcome:***

A case-report descriptive analysis will be done by reporting individual values of primary outcome according to the two periods as well as by using spaghetti plots showing the individual change from control to experimental period (by indicating the sequence of treatment). We also reported the mean, median and range values for control and experimental period. To assess the treatment effect (experimental vs. standard treatment) on primary outcome, we will use a Wilcoxon 'signed rank test. We will also report the standardized differences (Hedges'g) calculated from the within-patient's differences (E1-S2 and E2-S1) as effect size (calculated on rank transformed data).

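### The effect size that SAP section 2.3 plans to interpret for PTO comes with no confidence interval and no estimate in PTO points

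*SAP*

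**What the plan says.** - **Original basis for phase II (SAP 2.3).** The plan was for 20 analysable patients, sized for more than 80% power with a two-sided 5% test. The difference to be detected is "an absolute decrease in PTO of 10% in intervention period compared to control period". The assumed SD is 15% and the assumed within-patient correlation is 0.5. The target is therefore stated in PTO percentage points.
- **Revised basis (SAP 2.3).** When drug production capped the number at 12, that number was judged sufficient for first evidence of efficacy "by interpreting effect size on primary outcome and by a detailed descriptive analysis of changes in secondary outcomes in each period". The same section reports that only 9 patients have complete primary-outcome data. No power or precision is given for 12 or for 9.
- **Framework (SAP 2.4).** "Primary and secondary comparative objectives of phase II part of DIVE-1 trial are tested for superiority in favour of intervention".
- **Intervals (SAP 3.1).** "All confidence intervals (CIs) presented will be 95%CI and 2-sided". Tests are two-sided at 5%.
- **Primary analysis (SAP 5.2.2, Primary outcome).** "To assess the treatment effect (experimental vs. standard treatment) on primary outcome, we will use a Wilcoxon 'signed rank test". Individual values, spaghetti plots, and the mean, median and range for each condition are also reported, as is Hedges' g from the within-patient differences, computed after rank transformation. No interval is planned for g or for the PTO difference.
- **Other analyses (SAP 5.5 and 5.6).** None are planned, so nothing else fills the gap.

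**The concern.** Section 2.3 gives the effect size on PTO a real job: it is what makes a phase II smaller than planned worth interpreting. The quantity that section 5.2.2 delivers cannot do that job well. A standardised difference on ranks has no PTO unit, so it cannot be compared with the 10-point difference for which the study was sized. Without an interval, a reader cannot tell a moderate g that is well estimated from one that is compatible with no effect. At 9 patients the second case is the usual one. The interval rule in section 3.1 suggests that intervals will appear, but no phase II analysis produces one.

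At stake is the reading of the main phase II result. If the test is not significant, the report will contain a bare g and condition-level summaries, with no statement of which PTO differences the data support or exclude.

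**Working it through.** **Inputs, all from SAP 2.3.** Difference 10 points; SD 15; within-patient correlation 0.5; two-sided level 0.05; 20 patients planned, 12 after revision, 9 analysable.

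**Step 1: reproduce the plan's figure.**
- SD of the within-patient difference = 15 × √(2 × (1 − 0.5)) = 15.
- Standardised difference = 10/15 = 0.667.
- Paired t-test, n = 20: power 80.7%. The stated power above 80% is confirmed, and 20 is the smallest number that reaches it.

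**Step 2: precision in PTO points.** Half-width = t(0.975, n − 1) × 15/√n.

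| n | 95% half-width (PTO points) |
|---|---|
| 20 | 7.0 |
| 12 | 9.5 |
| 9 | 2.306 × 15/3 = 11.5 |

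At n = 9 the half-width exceeds the 10-point target.

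**Step 3: what an interval would add to g.** Suppose exactly the planned effect is observed at n = 9. The small-sample factor is 1 − 3/(4 × 8 − 1) = 0.903, so g = 0.667 × 0.903 = 0.60. The 95% interval (noncentral t, unranked differences) runs from about −0.07 to 1.24. A g of 0.60 alone looks like a moderate effect; the interval shows that it is compatible with none.

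**Step 4: how often g and the test point different ways.** The SAP sets no mark for a relevant g, so three are assumed here. The setting is n = 9, differences normal with SD 15, the exact signed-rank test, g on raw differences, and 200,000 simulated trials with the planned 10-point effect present.

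| Assumed mark for g | g at or above the mark, test not significant |
|---|---|
| 0.2 | about 55% |
| 0.5 | about 28% |
| 0.8 | about 1% |

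The SAP's g is on ranks, and the text does not say what is ranked. If it is the signed ranks of the nine differences, the figure at 0.5 is about 25% and at 0.8 it is nil.

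**Step 5: the interval that matches the test.** With ranks 1 to 9, the number of sign patterns with rank sum 0, 1, 2, 3, 4, 5 is 1, 1, 1, 2, 2, 3, a total of 10 out of 2⁹ = 512. Rejecting in both tails at that cut gives 20/512 = 3.9%, so the matching interval covers 96.1%. Rank sum 6 adds 4 patterns per tail: 28/512 = 5.5%, coverage 94.5%. So 96.1% is the attainable level closest to 95% from above.

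**The case against.** A reader might infer from sections 2.3 and 2.4 that there are two unranked routes to an efficacy claim, a test and an effect size, and that the sponsor may use whichever is favourable. The documents do not support this. Section 5.2.2 gives the assessment of the treatment effect to the signed-rank test and adds g as a further report. The revision table likewise names a non-parametric paired test with a case-report description as the primary efficacy analysis. The words in section 2.3 explain why a smaller number was accepted; they set no success rule. It follows that the 5% level still governs the primary test.

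Three further objections have weight.
- The disagreement rates depend on a mark that is not in the SAP, and at 0.8 they almost vanish. If g is computed on the signed ranks of nine untied, non-zero differences, the sum of squared ranks is fixed at 285 and g is a function of the test statistic. Significance then corresponds to |g| of about 0.81 or more, and the two cannot conflict in substance. This limits what Step 4 shows. It also means that such a g would add no information beyond the test and still nothing in PTO points.
- Section 3.1 only fixes the form of any interval that is presented; it does not promise one for phase II. That is correct, so this is an omission and not a breach.
- Individual values for nine patients make the spread visible. They do, but they do not give an estimate of the treatment difference with its uncertainty.

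Forbidding any statement based on an effect size would be a policy choice for a proof-of-concept phase, and it is not asked for here.

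**Conclusion.** The point holds as a gap between what section 2.3 intends to interpret and what section 5.2.2 produces. The planned effect size is on a rank scale, has no interval, and cannot be compared with the 10-point target. Under the plan's own assumptions (SD 15, correlation 0.5, 9 patients), the 95% half-width is about 11.5 points, so imprecision is a main feature of the result and should be shown. That figure rests on approximately normal differences and on the planning SD; the observed SD may differ. The 96.1% coverage assumes no ties or zero differences. The rates in Step 4 are illustrative and do not carry the conclusion.

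**What to change.** - **Section 5.2.2, Primary outcome:** add the Hodges-Lehmann estimate of the within-patient difference in PTO points (experimental minus standard), with the exact interval that inverts the signed-rank test. At n = 9 this runs from the 6th smallest to the 6th largest of the 45 pairwise averages, each difference being also paired with itself. Estimate, interval and test then agree by construction.
- **Section 3.1:** note that exact intervals are given at the smallest attainable level of at least 95%, which is 96.1% for nine patients.
- **Section 2.3:** say that the effect size is interpreted together with this interval, as support for the signed-rank test named in section 5.2.2.

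The cost is a few lines of text and one extra output; section 5.7 already allows R where needed. The downside for the sponsor is that a wide interval will make the evidence look less favourable than g alone.
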